### 9.4 Statistical Analyses

Statistical analysis will be performed using the computer program package SAS® System (release 9.2 or later version; SAS Institute, Cary NC, USA). Details on the statistical analysis will be presented in the integrated analysis plan prior to database lock.

The statistical analysis will not be started until all data have been corrected and checked for plausibility, and until all necessary coding and assessments have been completed.

Medical history and AE terms will be coded with the latest version of the Medical Dictionary for Regulatory Activities (MedDRA; version 22.0 or later); concomitant medication will be coded with WHO Drug Dictionary, WHO Drug Reference List and Anatomical Therapeutic Chemical Classification System, latest version. Versions of dictionaries used for coding will be defined in the Data Management Plan (DMP).

All data recorded during the study will be presented in individual data listings.

All data will be evaluated as observed, no imputation method for missing values will be used except for missing dates/times in AE data which will be performed for the classification of treatment-emergence, assigning AEs to treatment periods and for calculation of duration. The handling of concentration values below the limit of quantification will be described in the statistical analysis plan.

Summary statistics will be provided for all endpoints.

#### **9.4.1 Efficacy Analyses**

Not applicable.

#### **9.4.2 Safety Analyses**

In general, for the evaluation of safety parameters, the numerical values will be summarized descriptively (N, arithmetic mean, median, standard deviation, minimum and maximum values). Categorical variables will be presented in frequency tables by the number of observations and percentages.

Adverse event counts and participants with AEs will be summarized for each treatment by system organ class and preferred term. In addition, AEs will be tabulated and listed per participant and analyzed by severity and relationship to study drug.

Participants who prematurely withdrew from the study or from treatment will be displayed in a by-participant listing and summarized by primary withdrawal reason for each treatment sequence.

Safety laboratory parameters will be listed for each participant including changes from baseline and flags for measurements outside the reference ranges, where applicable. Laboratory parameters (hematology and clinical chemistry) will be summarized by time point including both absolute values and changes from baseline.

Vital signs and ECG parameters will be listed by participant including changes from baseline and summarized by treatment and time point using descriptive statistics. Physical examination assessments will be listed for each participant.

All safety analyses will be performed on the Safety Analysis population.

### 9.4.3 Other Analyses

The analysis of the primary endpoints  $AUC_{0-t}$  and  $C_{max}$  of rac-PZQ will be performed using the PK population. The analysis of the secondary endpoints  $AUC_{0-t}$  and  $C_{max}$  of R-(-)-PZQ and S-(+)-PZQ will use a similar approach.

For the analysis of  $AUC_{0-t}$  and  $C_{max}$ , a reference-scaled BE approach will be applied as follows:

The within-subject variability of the reference product will be calculated from a linear model fitted to the log-transformed PK parameters  $C_{max}$  and  $AUC_{0-t}$ , with sequence, subject within sequence, period included as fixed effects, described in Section 3.4 of Question 8 in [EMA/618604/2008 Rev. 13: Questions & Answers](#): positions on specific questions addressed to the Pharmacokinetics Working Party (PKWP). In this analysis, only participants with evaluable data from both administrations of the reference product will be included. If the within-subject coefficient of variation for the reference treatment ( $CV_{WR} \leq 30\%$  for  $C_{max}$  or  $AUC_{0-t}$  (i.e. the within-subject CV for the reference drug is  $\leq 30\%$ ), then the common acceptance range (80.00% to 125.00%) for BE will apply for the respective PK parameter. For  $30\% < CV_{WR} \leq 50\%$  the acceptance interval will be widened according to  $[L, U] = \exp(\mp k s_{WR})$ , where  $U$  is the upper limit of the acceptance range,  $L$  is the lower limit of the acceptance range,  $k$  is the regulatory constant set to 0.760 and  $s_{WR}$  is the intrasubject standard deviation of the log-transformed values of  $C_{max}$  or  $AUC_{0-t}$  of the reference product, and  $CV_{WR} = \sqrt{\exp(s_{WR}^2) - 1}$ .  $s_{WR}$  will be calculated using the data under reference treatment only. For all values of  $CV_{WR}$  greater than 50% the acceptance range is fixed to [69.84% to 143.19%].

An analysis of variance with treatment, period, sequence and subject within sequence as effects, will be fitted to log-transformed PK parameters  $AUC_{0-t}$  and  $C_{max}$  according to Method A in Question 8 in [EMA/618604/2008 Rev. 13](#). Only participants with at least one valid PK parameter under both reference and test treatment will be included in this model. Least-squares mean differences between treatments will be derived on the log-scale together with 90% confidence intervals.

Estimates and confidence intervals will be back-transformed to the natural scale. Bioequivalence will be accepted if, firstly, the back-transformed 90% confidence intervals are included in the acceptance range, and, secondly, the geometric mean ratios are contained in the conventional acceptance range 80.00% to 125.00%.

The estimated within-subject variability  $CV_{WR}$  may be inflated in the presence of outliers. In order to exclude such inflation, sensitivity analyses will be performed. In these analyses, outliers will be identified using graphical methods (such as plotting the PK parameter after the first administration against the corresponding value after the second administration) and/or statistical methods (such as identifying subjects whose studentized residuals fall outside the interquartile range), and the acceptance range will be based on  $CV_{WR}$  calculated with outliers removed from the dataset.

Descriptive statistics and boxplots for PK parameters of all analytes will be provided by treatment. Additional exploratory analyses will be described in the integrated analysis plan.

PK analyses will be specified in the Integrated Analysis Plan finalized before database lock.

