#### 4.2.2 Justification for using the reference scaled approach

When using a reference scaled approach to establish bioequivalence, the acceptance region of (0.80-1.25) for the confidence interval of the ratio of geometric means may be widened depending on the within-subject variability of the reference product. If the observed within-subject coefficient of variation is less than 30%, no scaling will be applied. For a coefficient of variation (CV) above 30%, scaled acceptance criteria will be applied. Details are described in Section 9.4.3. To support the request to apply a reference scaled approach also for AUC, the known variability as well as the effect for the therapeutic window/safety effect need to be taken into account.

a) Magnitude of observed variability for rac-PZQ.

The guidance document of 2015 issued by PQTm states the following: Information on rac-PZQ currently available to the PQTm indicates that the intrasubject variability for rac-PZQ is around 50–60% for  $C_{\max}$  and 35% for  $AUC_{0-t}$ .

The data from the first BE study showed that the observed intrasubject variability for rac-PZQ for  $C_{\max}$  and AUC for the reference formulation was respectively 47.08% and 33.4% while the overall CV% was above 60% for both  $C_{\max}$  and AUC for all 3 administrations.

b) Impact of widened acceptance criteria on safety and efficacy.

As of now, no clinical data are available that show a convincing correlation between exposure to rac-PZQ or R-(-)-PZQ and efficacy (characterized by cure rate as assessed by Kato-Katz method), neither in adults nor in children. At the time of registration in the seventies no proper dose-finding and efficacy studies were performed and the available PK data was obtained in a few healthy volunteers. Most data on efficacious doses have been gathered later from meta-analysis studies.

Recently, several meta-analyses have been performed showing quite an extensive overlap in efficacy in schistosomiasis treatment between a dose of 30, 40 and 60 mg/kg of rac-PZQ indicating a wide therapeutic range (Olliario 2011, Zwang 2014). From these data, combined with the overall acceptable safety of the compound even at high doses, it is expected that accepting a wider CI for showing BE will not affect the overall efficacy or the safety of the upgraded formulation.

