6.2 Final Analysis

The final, planned analyses identified in the CSP and in this IAP will be performed after the last participant has completed the last visit, i.e. end of treatment/safety follow-up visit with all trial data in-house, all data queries resolved, and the database locked.

A data review meeting will be held prior to database lock for the final analysis. In addition, no database can be locked until this IAP has been approved.

7 Changes to the Planned Analyses in the Clinical Study Protocol

There are no changes to the planned analyses in the CSP.

8 Protocol Deviations and Analysis Sets

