16.1.1 Planned Analyses of PK Parameter Data

The following PK parameter tables will be produced:

- Summary of PK parameters by treatment T1, T2, R1 and R2 of all analytes.

The following listing will be produced:

- Individual PK parameters listed by treatment T1, T2, R1, R2. Excluded PK parameters will be flagged.

The following figures will be produced for PK parameters:

- Boxplots for the C_{\max} and AUC_{0-t} by treatment T1, T2, R1, R2 of all analytes.

The analysis of the primary endpoints AUC_{0-t} and C_{\max} of rac-PZQ will be performed using the PK population. The analysis of the secondary endpoints AUC_{0-t} and C_{\max} of R-(-)-PZQ and S-(+)-PZQ will use a similar approach.

For the analysis of AUC_{0-t} and C_{\max} , a reference-scaled BE approach will be applied as follows:

The within-subject variability of the reference product will be calculated from a linear model fitted to the log-transformed PK parameters C_{\max} and AUC_{0-t} , obtained under reference treatment only, with sequence, subject within sequence, period included as fixed effects, described in Section 3.4 of Question 8 in [EMA/618604/2008 Rev. 13: Questions & Answers](#): positions on specific questions addressed to the Pharmacokinetics Working Party (PKWP). In this analysis, only participants with evaluable data from both administrations of the reference product will be included. If the within-subject coefficient of variation for the reference treatment ($CV_{WR} \leq 30\%$ for C_{\max} or AUC_{0-t} (i.e. the within-subject CV for the reference drug is $\leq 30\%$), then the common acceptance range (80.00% to 125.00%) for BE will apply for the respective PK parameter. For $30\% < CV_{WR} \leq 50\%$ the acceptance interval will be widened according to $[L, U] = \exp(\mp k s_{WR})$, where U is the upper limit of the acceptance range, L is the lower limit of the acceptance range, k is the regulatory constant set to 0.760 and s_{WR} is the intrasubject standard deviation of the log-transformed values of C_{\max} or AUC_{0-t} of the reference product, and $CV_{WR} = \sqrt{\exp(s_{WR}^2) - 1}$. s_{WR} will be calculated using the data under reference treatment only. For all values of CV_{WR} greater than 50% the acceptance range is fixed to [69.84% to 143.19%].

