An analysis of variance (ANOVA) with treatment, period, sequence and subject within sequence as fixed effects, will be fitted to log-transformed PK parameters AUC_{0-t} and C_{\max} according to Method A in Question 8 in [EMA/618604/2008 Rev. 13](#). Only participants with at least one valid PK parameter under both reference and test treatment will be included in this model. Least-squares mean differences between treatments will be derived on the log-scale together with 90% confidence intervals.

Estimates and confidence intervals will be back-transformed to the natural scale. Bioequivalence will be accepted if, firstly, the back-transformed 90% confidence intervals are included in the acceptance range, and, secondly, the geometric mean ratios are contained in the conventional acceptance range 80.00% to 125.00%.

The estimated within-subject variability CV_{WR} may be inflated in the presence of outliers. In order to exclude such inflation, sensitivity analyses will be performed. In these analyses, outliers will be identified using graphical methods by plotting the PK parameter after the first administration (R1) against the corresponding value after the second administration (R2), and/or statistical methods (such as identifying subjects whose studentized residuals fall outside the

interquartile range and/or outside the whiskers), and the acceptance range will be based on CV_{WR} calculated with outliers removed from the dataset.

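### The interquartile-range outlier rule in the CVwR sensitivity analysis removes half of the subjects from clean data, and the SAP's whisker wording does not replace it

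*Protocol*

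**What the plan says.** Protocol 9.4.3 warns that outliers may inflate CVwR and responds: "In order to exclude such inflation, sensitivity analyses will be performed". Outliers are to be found by graphical and/or statistical methods. The graphical method is a plot of the first against the second administration. The statistical example is "identifying subjects whose studentized residuals fall outside the interquartile range), and the acceptance range will be based on" the CVwR recomputed without those subjects. The same section adds that "PK analyses will be specified in the Integrated Analysis Plan finalized before database lock".

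SAP 16.1.1 takes up both methods. On the graphical side, "outliers will be identified using graphical methods by plotting the PK parameter after the first administration (R1) against the corresponding value" for R2, with no numeric cut-off. On the statistical side the interquartile-range criterion stays and gains an alternative: "interquartile range and/or outside the whiskers), and the acceptance range will be based on" the reduced dataset. The whiskers are not defined, and nothing says which of the two rules governs. SAP section 7 states: "There are no changes to the planned analyses in the CSP".

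CVwR itself comes from a model for the PK parameters "obtained under reference treatment only, with sequence, subject within sequence, period included as fixed effects", restricted to participants with both reference values. For the size to expect, Protocol 4.2.2 reports that in the first bioequivalence study the within-subject CV of Cmax and AUC "for the reference formulation was respectively 47.08% and 33.4" percent.

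**The concern.** An outlier rule should flag few or no subjects when there are no outliers. The interquartile range is the middle half of the data, so a rule that flags everything outside it flags the other half whatever the data look like. Because *and/or* lets the statistical method be used alone, the plan permits this rule to decide the sensitivity analysis.

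The SAP's addition does not repair it. Every residual beyond a box-plot whisker is also outside the box. Read as *or*, the combined wording is therefore just the interquartile-range rule; read as *and*, it is just the whisker rule. The two readings differ greatly in what they remove, and the choice can still be made after the data are seen.

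Reference scaling for both Cmax and AUC is central to this design. The outlier analysis is the plan's own safeguard that any widening of the limits reflects real variability. If its statistical branch collapses CVwR in clean data, it can contradict a sound primary result. Neither document says how such a contradiction would be read.

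**Working it through.** **Inputs.** From Protocol 9.4.3 and SAP 16.1.1: k = 0.760, no widening at CVwR ≤ 30%, and a cap of 69.84–143.19% above 50%. From Protocol 4.2.2: CVwR 47.08% (Cmax) and 33.4% (AUC). From Protocol 7.2: 36 randomized, at least 32 evaluable. Assumed, because the documents do not say: residuals come from the reference-only model, and whiskers are 1.5×IQR.

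**1. The plan's own figure.** s = √ln(1 + CV²) and limits = exp(∓0.760·s). At CV 50%, s = √ln 1.25 = 0.4724 and 0.760 × 0.4724 = 0.3590, giving 69.84–143.19%, as stated.

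**2. Limits without removal.** Cmax: s = 0.4474, limits 71.17–140.50%. AUC: s = 0.3252, limits 78.10–128.04%.

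**3. Who is flagged.** With two reference values per subject and period effects fitted within sequence, a subject's residuals are +r and −r. The pooled residuals are then symmetric about zero, so Q1 = −Q3, and Q3 is the median of |r|. A subject is flagged when |r| exceeds that median. That is half of the subjects: 16 of 32, or 18 of 36.

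**4. Effect on CVwR for normal log-data.** A normal variable cut at its quartiles (q = 0.6745, density 0.3178) keeps a fraction √(1 − 2·q·0.3178/0.5) = 0.378 of its SD.
- Cmax: 0.378 × 0.4474 = 0.169, so CVwR = √(exp(0.169²) − 1) = 17.0%.
- AUC: 0.378 × 0.3252 = 0.123, so CVwR = 12.3%.

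Both are far below 30%, so the range returns to 80.00–125.00%.

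**5. Simulation of clean trials.** n = 32, balanced and complete, s² on n − 2 = 30 df, CVwR recomputed on the subjects kept. With no removal the median CVwR is 46.5% (Cmax) and 32.9% (AUC). Discordance means that the primary analysis passes and the sensitivity analysis fails. It uses the Method A 90% CI and the 80–125% GMR constraint. It also assumes true ratios of 0.90 / 0.95 / 1.00, equal test and reference variability, and no subject-by-formulation interaction.

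| | IQR rule | 1.5×IQR whiskers |
|---|---|---|
| Subjects flagged | 50%, every trial | 1.4%; at least one in about 29% of trials |
| Median CVwR, Cmax | 16.8% (95% range 10.0–25.9%) | 44.2% |
| Median CVwR, AUC | 12.2% (95% range 7.2–18.5%) | 31.6% |
| Widening lost where present, Cmax | 99.7% | about 3% |
| Widening lost where present, AUC | 100% | 17–18% |
| Discordance, Cmax | 50% / 31% / 24% | 5% / 3% / 2% |
| Discordance, AUC | 17% / 5% / 2% | 4% / 1% / 0.3% |

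For AUC about a quarter of clean trials have no widening to lose: P(χ²₃₀ ≤ 30 × ln 1.09 / ln(1 + 0.334²)) = P(χ²₃₀ ≤ 24.4) = 24.8%. At the other CVs quoted in Protocol 4.2.2, the IQR rule loses widening in 100% (AUC 35%), 99.2% (Cmax 50%) and 94.6% (Cmax 60%) of the trials that had it.

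**The case against.** The criterion is introduced as an example and belongs to a sensitivity analysis. The point estimate, the confidence interval and the GMR constraint do not use it. Removing the subjects with the largest residuals narrows the limits, so the rule cannot create a false claim of bioequivalence. By adding whiskers the SAP signals that a box-plot rule was probably meant, and an analyst who saw half of the subjects deleted would notice. If the whisker reading is adopted at 1.5×IQR, discordance is at most 5%. The Cmax discordance figures for the IQR rule rest on true ratios that the public text does not give. Elaborating an example in the SAP, to which the protocol defers, is not in itself an undeclared change.

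Most of this stands, and it limits the weight of the point. It does not remove it. The criterion is the only statistical method the protocol names. The SAP, which was meant to settle the detail, repeats it and leaves the *or* reading available. Probable intent is not a prespecified rule, and the plot offers no numeric criterion to fall back on. That the all-data CVwR sets the primary range is a reasonable inference from the word *sensitivity*, but neither document says so outright. The whisker figures also depend on the quartile convention: averaged order statistics give 1.25% of subjects flagged and 16% of AUC widening lost. The contrast with 50% is unchanged.

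**Conclusion.** The point holds: the interquartile-range criterion is wrong as written, and the SAP does not correct it. That it flags half of the subjects follows from the definition of quartiles and the mirrored residuals, and needs no distributional assumption. The fall in CVwR to about 17% (Cmax) and 12% (AUC0-t), and the near-certain loss of widening, assume log-normal data without outliers at the first study's CVs. The discordance rates depend in addition on the assumed ratios and variances.

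The damage is confined to the sensitivity analysis. Its statistical branch cannot distinguish inflated from genuine variability, and its result turns largely on a choice left open until after the data are seen. It should be fixed before database lock, but it does not threaten the primary conclusion.

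**What to change.** In SAP 16.1.1 delete the interquartile-range criterion and name one rule. For example: a subject is an outlier if a studentized residual from the reference-only model lies below Q1 − 1.5×IQR or above Q3 + 1.5×IQR. State the type of studentized residual and the quartile method, and keep the R1-versus-R2 plot as a supporting display. Say that the all-data CVwR sets the primary acceptance range, that the CVwR without outliers sets the sensitivity range, and how a discordant result will be interpreted. Clarify Protocol 9.4.3 to match or, if the protocol is not reopened, record the departure in SAP section 7.

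The multiple is a choice, since the documents give none, and it has a trade-off. AUC0-t is expected close to 30%, so the 1.5× rule still loses widening in 17–18% of clean trials that had it, against about 6% at 2× and 0.5% at 3×. Longer whiskers miss real outliers. With two planted subjects (assumed 6-fold R2/R1 shift, true CVwR 25%), detection was about 95%, 83% and 42% at 1.5×, 2× and 3×. Depending on the sequence and direction of the two subjects, it ranged over 70–90% at 2× and 25–55% at 3×. For this reason the sensitivity result should not automatically override the primary decision.

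The cost is one or two sentences in the SAP plus the protocol clarification or section 7 entry. No extra data or participants are needed.

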#### 9.4.4 Sequence of Analyses

All final, planned analyses identified in the Clinical Study Protocol will be performed only after the last participant has completed the last visit, i.e. follow-up/end of study visit with all study data in-house, all data queries resolved, and the database locked.

## Appendix 1 Abbreviations

AE	Adverse Event
AUC	Area under the concentration-time curve
AUC 0-t	Area under the concentration-time curve from time zero to the last sampling time
BE	Bioequivalence
C max	Maximum observed concentration
CRF	Case Report Form
CRO	Contract Research Organization
CV	Coefficient of variation
CV WR	Within-subject coefficient of variation for the reference treatment
ECG	Electrocardiogram
GCP	Good Clinical Practice
GI	Gastrointestinal
ICF	Informed consent form
ICH	International Council for Harmonization
IEC	Independent Ethics Committee
IMP	Investigational-medicinal product
IRB	Institutional Review Board
PK	Pharmacokinetics
PQTm	Prequalification Team Medicines
PZQ	Praziquantel
SAE	Serious Adverse Event
SoA	Schedule of Activities
SUSAR	Suspected unexpected serious adverse reaction
TEAE	Treatment-emergent adverse event
VCT	Verified Clinical Trials
vs	Versus

## Appendix 2 Study Governance

### Financial Disclosure

Investigators and Sub-Investigators will provide the Sponsor with sufficient, accurate financial information, as requested, for the Sponsor to submit complete and accurate financial certification or disclosure statements to the appropriate regulatory authorities. This information is required during the study and for 1 year after completion of the study.

